#### **2.7.6.2 Slit lamp**

For each considered evaluation type in the CRF page and eye side, the number & percentage of subjects with and without abnormality (normal, insignificant, clinically significant) will be provided by timepoint and treatment arm. In addition, for each slit lamp evaluation, shift tables will be generated to present the worst post-baseline changes compared to baseline by treatment arm and eye side. Further, shift tables will be generated by visit, treatment arm and eye side. A listing of patients with any abnormality will be provided.

#### **2.7.6.3 Tonometry**

Descriptive statistics for the intraocular pressure at baseline, at each post-baseline visit and changes from baseline at each post-baseline visit will be presented, by eye and treatment arm. Box plot for intraocular pressure by eye side and treatment arm will be generated for the overall period.

The number & percentage of subjects with post-baseline values listed below will be summarized by treatment arm

- *at least one post-baseline* value  $\leq 5$  mmHg,  $> 5$  to  $\leq 21$  mmHg,  $> 21$  to  $\leq 30$  mmHg, and  $> 30$  mmHg by eye side (right, left, worst)
- the Increase from baseline IOP  $\geq 5$  mmHg to  $< 10$  mmHg &  $\geq 10$  mmHg by eye side (right, left, best)
- the Decrease from baseline IOP  $\geq 5$  mmHg to  $< 10$  mmHg &  $\geq 10$  mmHg by eye side (right, left, worst)

A listing of patients will also be provided for this assessment.

Intraocular pressure will also be summarized in shift table (baseline and post baseline value at each time point) for each eye side considering the following categories:  $\leq 5$ ,  $> 5$  to  $\leq 21$ ,  $> 21$  to  $\leq 30$  and  $> 30$  mmHg for each of the treatment arms.

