### **Tonometry**

Descriptive statistics of the intraocular pressure at baseline, at each post-baseline visit and changes from baseline at each post-baseline visit will be presented, by eye and treatment group.

The number of patients with clinically relevant changes from baseline intraocular pressure above 5 mmHg and 10 mmHg will be summarized by treatment arm. For patients with such values, a listing will also be provided.

Intraocular pressure will also be summarized in shift table (baseline and worst post baseline value) for each eye side considering the following categories:  $< 22$ ,  $\geq 22$  and  $< 30$  and  $\geq 30$  mmHg.

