### 2.7.6.1 Visual acuity

Visual acuity will be measured using the Snellen visual acuity. This is determined by establishing the smallest optotypes that can be identified correctly by the patient at a given observation distance. Snellen visual acuity can be reported as a Snellen fraction (m/M) in which the numerator (m) indicates the test distance and the denominator (M) indicates the distance at which the gap of the equivalent Landolt ring subtends 1 minute of arc. The following formula for conversion from Snellen acuity results to the logMAR score (Holladay 1997) will be applied and the LogMAR score will be calculated for each timepoint:

$$\text{logMAR score} = -\log_{10}(m/M).$$

The logMAR scores will be categorized as follows: < 0.1,  $\geq 0.1$  to < 0.2,  $\geq 0.2$  to < 0.3,  $\geq 0.3$  to < 0.6,  $\geq 0.6$ . The following shift tables will be generated using the above categories by treatment group:

- Comparing baseline and *increases* from baseline in logMAR score category at each visit by eye side (right & left)
- Comparing baseline and *decreases* from baseline in logMAR score category at each visit by eye side (right & left)

Change from baseline (logMAR) = Post Baseline Value (logMAR) – Baseline Value (logMAR)

In case both values are negative, the absolute values of Post baseline & Baseline records will be used for the calculation.

The number and percentage of subjects with the following change from baseline for logMAR categories (< 0.1,  $\geq 0.1$  to < 0.2,  $\geq 0.2$  to < 0.3,  $\geq 0.3$  to < 0.6,  $\geq 0.6$ ) will be summarized by treatment arm:

- the best change (decrease) in logMAR score category from baseline by eye side (right, left, best)
- the worst change (increase) in logMAR score category from baseline by eye side (right, left, worst)

The changes from baseline at each visit will be calculated for assessments done in the same correction method as at baseline.

The shift tables and summaries will be produced for the Safety set 4.

A listing with the Snellen fraction, logMAR score abnormalities and change from baseline categories will be provided for all subjects.

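### The only combined-eye row for rises in intraocular pressure is labelled 'best' eye; on its ordinary reading, patients with a relevant rise in at least one eye are not directly reported

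*SAP*

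**What the plan says.** The final SAP (21-Feb-2024), section 2.7.6.3 Tonometry, sets the unit of count: "The number & percentage of subjects with post-baseline values listed below will be summarized by treatment arm". Three bullets follow.

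- Absolute IOP in four categories, for the right, left and worst eye.
- "the Increase from baseline IOP" in two bands (5 to under 10 mmHg; 10 mmHg or more), "mmHg by eye side (right, left, best").
- "the Decrease from baseline IOP" in the same two bands, "mmHg by eye side (right, left, worst").

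Section 2.7.6.1 Visual acuity has a parallel pair of bullets. There the decrease in logMAR is called the best change and is given for right, left and best eye. The increase is paired the other way: "the worst change (increase) in logMAR score category from baseline by eye side (right, left, worst").

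Neither word is defined for IOP. The primary-analysis SAP (Amendment 3), section 2.9.2, counted patients with "clinically relevant changes from baseline intraocular pressure above 5 mmHg and 10 mmHg", and the End of Core SAP, section 2.9.6, kept the 5 and 10 mmHg thresholds. Neither names an eye-selection rule for that count.

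**The concern.** In the acuity section the order is favourable change with 'best', then unfavourable change with 'worst'. Tonometry has the same order of labels, but its first change bullet is the increase. The layout looks carried over without checking that the direction still matched the label, and no reason is given for a best-eye summary of rises.

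The matter at stake is a patient-level safety count. A reader who wants to know how many children had a relevant pressure rise in at least one eye would look to the row that combines the eyes. If that row shows the better eye, it answers a different question (how many rose in both) and could be mistaken for the patient-level result. Amendment 6 of the protocol was prompted mainly by a health authority request for ophthalmic data on ocular safety, so the ocular tables are likely to be read closely.

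**Working it through.** The plan states no figure here, so there is nothing to reproduce. The check applies the row rule to examples and then asks what can be recovered.

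**Inputs.** The bands and eye labels come from final SAP 2.7.6.3. The ordinary reading of the labels is an assumption: best-eye rise = min(right, left), worst-eye rise = max(right, left).

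**Step 1: the rule applied to made-up changes (mmHg).**

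| Right / left | Smaller rise | Band in 'best' row | Larger rise | Band in a 'worst' row |
|---|---|---|---|---|
| 12 / 1 | 1 | none | 12 | ≥10 |
| 7 / 0 | 0 | none | 7 | 5 to <10 |
| 12 / 6 | 6 | 5 to <10 | 12 | ≥10 |
| 11 / 11 | 11 | ≥10 | 11 | ≥10 |

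A rise in one eye only is absent from the 'best' row. An asymmetric rise in both eyes is placed one band too low. Only symmetric rises agree.

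**Step 2: can the any-eye count be derived?** For a threshold t,

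N(either eye ≥ t) = N(right ≥ t) + N(left ≥ t) − N(both ≥ t).

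If 'best' means the smaller of the two eyes' maximum rises, the 'best' row is the last term. With assumed rates of 5% per eye and 2% in both eyes, 5% + 5% − 2% = 8% have a rise in at least one eye, and the 'best' row shows 2%. For t = 5 mmHg the two bands are added first.

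This works only if both eyes are measured and each eye is banded once. It fails if the best eye is picked visit by visit. Take a patient with +12 right and 0 left at one visit, then 0 right and +11 left at another. The patient counts once in the right row, once in the left row and not at all in the 'best' row, so 1 + 1 − 0 = 2 for one patient. Section 2.7.6.3 does not say which rule applies.

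**Step 3: do other outputs fill the gap?** The worst-eye absolute row and the by-eye shift tables share a category running from above 5 to 21 mmHg. A one-eye rise from 9 to 20 mmHg is +11 but stays inside it, so neither shows the rise. The right or left change row and the by-eye change statistics include it, and the tonometry listing can show it for the patient.

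**Step 4: how far could the row differ?** The documents give no rates or between-eye correlation, so both are assumed. Under a bivariate normal model with per-eye rate p and correlation ρ, both = Φ₂(z_p, z_p; ρ), either = 2p − both, and share missed = 1 − both/either (computed before rounding).

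| p | ρ | Both ('best' row) | Either ('worst' row) | Share missed |
|---|---|---|---|---|
| 5% | 0 | 0.25% | 9.75% | 97.4% |
| 5% | 0.9 | 3.19% | 6.81% | 53.2% |
| 10% | 0 | 1.00% | 19.00% | 94.7% |
| 10% | 0.9 | 6.89% | 13.11% | 47.5% |
| 20% | 0 | 4.00% | 36.00% | 88.9% |
| 20% | 0.9 | 14.99% | 25.01% | 40.0% |

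These figures illustrate the rule; they are not estimates for this trial.

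**The case against.** The strongest reply is that 'best' is undefined, so an undercount is not established. In the acuity section the third row is arguably the eye with the largest change in the named direction, for decreases and increases alike. If tonometry follows that pattern, the increase row could be the eye with the largest rise under a wrong label, and a one-eye rise would be counted. Table layouts are in separate shells, which might settle this. That stands: the SAP text supports 'ambiguous or mislabelled', and an undercount follows only on the ordinary reading. It does not remove the need for a change, because a row of largest rises should not be called 'best'.

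A reader might also infer that the any-eye count is lost. The documents do not support that. On the ordinary reading the 'best' row supplies the overlap, so right + left − best may give the count under the conditions in Step 2, and the listing allows a direct count. What remains is that a headline safety number should not have to be reconstructed under unstated conditions.

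Three further inferences go too far. One-eye rises do not vanish from the report; Step 3 shows where they remain. The primary-analysis SAP does not single out rises: it speaks of relevant changes, without a direction. And 'worst' for decreases is not itself a fault, since the section also tabulates very low pressures (5 mmHg or below).

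**Conclusion.** The point holds in limited form. The increase row carries a label that conflicts with the acuity section and with the first tonometry bullet, and the label is undefined. On its ordinary reading, the row omits one-eye rises and puts asymmetric rises in a lower band, so the table does not directly report patients with a relevant rise in at least one eye.

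This rests on two assumptions: that a rise is the unfavourable direction, and that 'best' therefore means the smaller rise. A reader might take a multiple such as 8% against 2% as the size of the error, but it comes from assumed rates, and the assumed range in Step 4 is wide. The size in this trial is unknown. The effect is confined to one row of a descriptive safety table; no test, endpoint, error rate or sample size is touched.

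**What to change.** In final SAP 2.7.6.3, change 'best' to 'worst' in the increase bullet and define it as the largest rise in either eye. Leave the decrease bullet as 'worst', defined as the largest fall in either eye. With each row showing the larger change in its own direction, the table no longer depends on what 'best' means. It would help to say that the largest change is taken over all on-treatment values, in line with the rule for worst post-baseline assessments in section 5.3.4.

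The cost is one word, a short definition and the matching table shell. If the table has already been produced, one row needs to be rerun; no new data are required.

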#### **2.7.6.4 Lens photography**

The lens photography was collected for central reading to determine LOCSIII grade. A decimal grade using 0.1 unit intervals were assigned to the opacity by the grader. These continuous values ranging from 0.1 (clear or colorless) to 5.9 (very opaque for Cortical and Posterior

Subcapsular) or 6.9 (very opaque or brunescent for Nuclear Color, Nuclear Opalescence) were converted to standard grades using the [Table 2-2](#) (Chylack et al., 1993).

**Table 2-2 Standard grades for LOCSIII assessment**

Nuclear Color (NC)	Nuclear Opalescence (NO)	Cortical (C)	Posterior Subcapsular (P)
No Opacity is $\geq 0.1$ to $<1$			
NC1 is $\geq 1$ to $<2$	NO1 is $\geq 1$ to $<2$	C1 is $\geq 1$ to $<2$	P1 is $\geq 1$ to $<2$
NC2 is $\geq 2$ to $<3$	NO2 is $\geq 2$ to $<3$	C2 is $\geq 2$ to $<3$	P2 is $\geq 2$ to $<3$
NC3 is $\geq 3$ to $<4$	NO3 is $\geq 3$ to $<4$	C3 is $\geq 3$ to $<4$	P3 is $\geq 3$ to $<4$
NC4 is $\geq 4$ to $<5$	NO4 is $\geq 4$ to $<5$	C4 is $\geq 4$ to $<5$	P4 is $\geq 4$ to $<5$
NC5 is $\geq 5$ to $<6$	NO5 is $\geq 5$ to $<6$	C5 is $\geq 5$ to $\leq 5.9$	P5 is $\geq 5$ to $\leq 5.9$
NC6 is $\geq 6$ to $\leq 6.9$	NO6 is $\geq 6$ to $\leq 6.9$		

The worst change in grade compared to baseline for each eye, evaluation type, and treatment arm will also be presented using shift tables. For each considered evaluation type and eye side, the number & percentage of subjects for image quality will be provided by timepoint and treatment arm. A listing of subjects will be provided, additionally, listings for the findings, general comments and confidence score comments will be presented for safety set 3. As data was not analyzed so far, the analysis will be repeated for safety set 1 to 3.

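### Lens opacity is graded to 0.1 unit, but change from baseline is tabulated only on whole grades, so +0.9 can show as no change and +0.1 as a full grade worse

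*SAP*

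**What the plan says.** Final SAP section 2.7.6.4 (Lens photography) describes the reading as follows: "A decimal grade using 0.1 unit intervals were assigned to the opacity by the grader". The scale is introduced with "These continuous values ranging from 0.1 (clear or colorless) to 5.9" for cortical and posterior subcapsular opacity, and runs to 6.9 for nuclear color and nuclear opalescence. The values "were converted to standard grades using the" bands of Table 2-2 (Standard grades for LOCSIII assessment). Each band is one unit wide and includes its lower limit: 0.1 to below 1 is No Opacity, 1 to below 2 is grade 1, 2 to below 3 is grade 2, and so on.

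The only analysis of change is this: "The worst change in grade compared to baseline for each eye", by evaluation type and arm, set out in shift tables. The other lens outputs are image-quality counts by timepoint and listings: "A listing of subjects will be provided, additionally, listings for the findings, general comments and confidence score comments". No summary of change on the decimal scale is specified, and no minimum decimal change is defined.

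The neighbouring ocular sections work differently. For intraocular pressure, section 2.7.6.3 (Tonometry) has descriptive statistics in which "changes from baseline at each post-baseline visit will be presented, by eye and treatment arm", in addition to a shift table. For visual acuity, section 2.7.6.1 subtracts baseline logMAR from the post-baseline value first and puts the difference into categories afterwards.

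**The concern.** Categorising first and comparing afterwards makes the recorded change depend on where the baseline reading happens to sit inside its band. Progression inside a band disappears from the table. One step of the reader's scale across a band edge counts as a whole grade. Taking the worst post-baseline value gives each eye several chances to cross an edge through reading variation alone.

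Lens opacities are listed in Protocol Table 6-2 among disturbances reported with deferasirox. Protocol Amendment 6 introduced central reading of the photographs in response to a Health Authority request for ophthalmic data. Final SAP section 2.7.6 states that these readings have not been reported before. The table is therefore the first arm-level summary of the measure, and it should be able to show both early progression and its absence.

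**Working it through.** **1. The conversion is a floor.** Applying the Table 2-2 cut-points to every possible reading (0.1 to 6.9 for the nuclear scales, 0.1 to 5.9 for the other two) gives grade = floor(decimal) throughout, with grade 0 standing for No Opacity.

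**2. Worked pairs.** These need no assumption.

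| Baseline to follow-up | Decimal change | Grade change |
|---|---|---|
| 1.0 to 1.9 | +0.9 | 0 |
| 1.9 to 2.0 | +0.1 | +1 |
| 0.1 to 0.9 | +0.8 | 0 (stays No Opacity) |
| 0.9 to 1.0 | +0.1 | +1 (new opacity) |

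Over all pairs that worsen or stay the same, a grade change of 0 covers decimal changes of 0.0 to 0.9, and a grade change of +1 covers 0.1 to 1.9. The two ranges overlap almost completely.

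**3. True worsening that is missed.** Assume, for illustration only, that baselines are spread evenly over the nuclear scale of 69 values.
- A +0.5 change has 64 possible baselines, of which 30 cross an edge: 30/64 = 47% show a shift and 53% show none.
- A +0.1 change has 68 possible baselines, of which 6 cross: 6/68 = 9% show a full grade.
- A +0.9 change has 60 possible baselines, of which 6 do not cross: 6/60 = 10% show no change.

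**4. False shifts from reader variation.** The documents give neither reader repeatability nor a baseline distribution, so both are assumed and varied. The simulation used 400,000 eyes with no true change. Each reading was the true value plus normal error, rounded to 0.1 and not allowed below 0.1. Baseline and follow-up were read independently, with three post-baseline visits. Three matches the scheduled photographs through Week 101 in Protocol Table 7-3 (Week 25, end of core, Week 101). The table gives the percentage of eyes with an upward grade shift at the worst of three visits.

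| True baseline spread over | SD 0.1 | SD 0.2 | SD 0.3 |
|---|---|---|---|
| 1 to 4 | 10 | 21 | 31 |
| 0.1 to 1.0 | 9 | 17 | 24 |
| 0.1 to 0.7 | 0.1 | 4.6 | 13 |
| 0.1 to 0.5 | 0.0 | 0.6 | 6 |

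**5. The same data on the decimal scale.** An increase of at least 1.0 at the worst of three visits occurs by chance in 0%, 0.1% and 3.3% of eyes for baselines over 1 to 4, and no more often in the other rows. An increase of at least 0.5 occurs in 0.3%, 13% and 30% for baselines over 1 to 4, and in 0.1%, 9% and 23% for baselines over 0.1 to 0.5.

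**The case against.** The strongest objection is to the size. The larger false-shift rates need baselines spread well up the scale or close to the first cut. Patients were 2 to under 18 years old at enrolment, and the scale's bottom band is No Opacity. If most lenses start at 0.1 to 0.5, the planned table gives few false shifts. This stands. A reader might infer from step 4 that a tenth to a third of eyes will be reported as spuriously worse. The documents do not support that, because they give no baseline distribution and no reader error. With clear lenses the main loss is the opposite one: progression within No Opacity goes unseen.

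A second objection is that a decimal threshold is not automatically better. This also stands for low thresholds. With baselines at 0.1 to 0.5, a cut of 0.5 gives more chance events than the planned shift table (23% against 6% at SD 0.3).

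Third, baseline-to-worst shift tables are this SAP's usual safety display, and the grade bands come with a cited reference. Whether that reference supports measuring change on converted grades cannot be checked from the documents. The point does not rely on it, because the grade table can stay.

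Fourth, lens safety does not rest on this table alone. Slit-lamp shift tables, visual acuity changes and adverse event reporting also bear on it. The subject listing may show decimals, and the word also in the shift-table sentence may hint at another summary. The SAP specifies neither, and a listing is not a summary by arm. It would be too strong to say that the decimals are lost, since nothing says they are dropped from the data.

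**Conclusion.** The point holds as a minor one. From the SAP text alone, the only specified measure of lens change can rank a +0.1 change above a +0.9 change. The tonometry and visual acuity sections of the same SAP avoid this.

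The size is uncertain. At the worst of three visits, false upward shifts range from about 0% to 31%, depending on an assumed reader SD of 0.1 to 0.3 and an assumed baseline range. The share of true +0.5 changes that go unseen is about half if baselines are evenly spread.

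The output is descriptive, and no hypothesis test or success criterion uses it. A reader might infer that the lens safety conclusions are invalid or that one arm is favoured. Neither follows: the same conversion applies to both arms, other ocular assessments are reported, and the defect is a loss of information in one table.

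**What to change.** Keep the Table 2-2 grade shift table. In final SAP section 2.7.6.4, add:
- descriptive statistics of change from baseline in the decimal grade (post-baseline minus baseline), for each eye and lens evaluation type, by visit and treatment arm, as section 2.7.6.3 does for intraocular pressure;
- the number and percentage with a worst post-baseline decimal increase of at least 1.0, which chance alone produces in about 3% of eyes or fewer in the scenarios above.

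The by-visit statistics show progression inside a band, and they do not depend on the worst value. A lower threshold such as 0.5 should be added only if reader repeatability supports it, since at a reader SD of 0.3 chance alone can exceed it in up to about 30% of eyes.

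The cost is one extra table from readings already collected.

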### **2.7.6.5 Fundus oculi**

For each eye side, the number & percentage of subjects with and without abnormality (normal, insignificant, clinically significant) will be provided by timepoint, eye side and treatment arm. In addition, shift table will be generated to present the worst post-baseline changes compared to baseline by eye side and treatment arm. A listing of subjects with any abnormality will be provided.

### **2.7.6.6 Color Fundus Photography**

The Color Fundus Photography Assessment will be conducted by a central vendor through photographs. For each considered evaluation type and eye side, the number & percentage of subjects with and without abnormality will be provided by timepoint and treatment arm. For each considered evaluation type and eye side, the number & percentage of subjects for image quality will be provided by timepoint and treatment arm. A listing of subjects will be provided, additionally, listings for the findings, general comments and confidence score comments will be presented for safety set 3. As data was not analyzed so far, the analysis will be repeated for safety set 1 to 3.

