## Amendment 6 (24-Jun-2021)

### Amendment rationale

As of 24-Jun-2021, 67 patients are ongoing in the extension phase of the study. All patients had completed the Core phase of the study by 18-Dec-2018. The primary analysis for this study was completed on 07-Dec-2018 (data cut-off date 31-May-2018).

The main purpose of this amendment is to introduce the requirement for central collection and assessment of photographs from ocular examinations (lens photographs and wide angle fundus photographs) collected during the study by a Novartis designated imaging Contract Research Organization (CRO). This change is in response to a Health Authority request to submit CALYPSO ophthalmic data (for up to 2 years of follow up) to support the ocular safety evaluation of deferasirox.

Clarification was also added to state that for patients who need correction, the best corrected visual acuity should be tested when performing the distance visual acuity test and that the corrected visual acuity should be documented in the source records.

In addition, mitigation procedures have been implemented throughout the protocol to ensure participant safety and trial integrity during a Public Health emergency, as declared by Local or Regional authorities i.e. pandemic, epidemic or natural disaster.

Finally, assessment of the study Risk/Benefit in light of the ongoing coronavirus disease 2019 (COVID-19) pandemic at the time of this protocol amendment concluded that there are no additional risks related to COVID-19 for this study. Patient with cytopenias are more susceptible to infections in general, compared to patients without cytopenias. There have been postmarketing reports of cytopenias in patients treated with deferasirox and patients with cytopenias may be at higher risk of COVID-19 with a poorer prognosis. The periodic monitoring of blood counts and interruption of study treatment in patients who develop unexplained cytopenia, as defined in the protocol, are expected to mitigate this risk.

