#### **7.2.4.5 Ocular Examination and Central Imaging Assessment**

Patients will undergo ophthalmologic examinations during the core phase at Visit 1, 11, 777 (EOT Core) and at unscheduled visits (if needed). During the optional extension phase, assessments will be done annually as per Exjade prescribing information and at EOT of Extension phase.

The ophthalmologic examination includes the following assessments:

- Distance visual acuity test: in patients who don't need correction with glasses or contact lenses, visual acuity test may be performed without correction. In patients who need correction (either wears prescription glasses/contact lenses or uncorrected visual acuity is not within normal limits), best corrected visual acuity should be tested. Information about visual acuity without correction, best corrected visual acuity and prescription/correction must be documented in the source records.
- Applanation tonometry
- Slit Lamp exam and lens photography
- Fundus exam and wide angle fundus photography of the retina and optic nerve

Interpretation of the ocular examinations must be made by a qualified physician and documented on the CRF page.

Information about the results of the ocular examinations, including the lens photographs and the wide angle fundus photographs of the retina and optic nerve, must be present in the source documentation at study site. Significant findings of the ocular examinations that meet the definition of an AE must be recorded in the adverse event summary page of the case report form.

All screening and on-study wide angle fundus photographs and lens photographs, including photography acquired prior to the release of Protocol Amendment 6, must be sent to an imaging Contract Research Organization (CRO) designated by Novartis for central assessment.

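### The final SAP plans no baseline shift for centrally read fundus photographs, so its summary tables show prevalence of abnormality but not new abnormalities

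*SAP*

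**What the plan says.** Final SAP Section 2.7.6.6 gives the centrally read fundus photographs one findings summary: for each evaluation type and eye side, the "number & percentage of subjects with and without abnormality will be provided by timepoint" and by treatment arm. A parallel table covers image quality. The section then adds: "A listing of subjects will be provided, additionally, listings for the findings, general comments and confidence score comments will be presented for safety set 3". Because these data had not been analysed before, the work is repeated on Safety Sets 1 to 3 in addition to Safety Set 4, the default in Section 2.7.6. No shift table, change from baseline or category for new or worsened findings is named.

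The two neighbouring sections do name one. For the centrally read lens photographs (Section 2.7.6.4): "The worst change in grade compared to baseline for each eye, evaluation type, and treatment arm will also be presented using shift tables". For the site's own fundus examination (Section 2.7.6.5), a "shift table will be generated to present the worst post-baseline changes compared to baseline by eye side and treatment arm".

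Baseline images belong to the central read. Protocol Section 7.2.4.5 requires that "All screening and on-study wide angle fundus photographs and lens photographs, including photography acquired prior to the release of Protocol Amendment 6" go to the imaging vendor, and Table 7-3 marks the screening photographs as required. The Amendment 6 rationale says that the ophthalmic data were requested by a Health Authority, for up to two years of follow-up, "to support the ocular safety evaluation of deferasirox".

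**The concern.** A safety reader of fundus photographs wants to know how many eyes that were normal at the start became abnormal on treatment, and whether that differs between arms. A percentage abnormal at each visit does not answer this. It mixes findings present before treatment, findings that appeared, findings that resolved, and changes in who was imaged.

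The omission stands out for three reasons. All other modalities in Section 2.7.6 have a baseline comparison. Table 1-1 of the final SAP names LOCSIII and the colour fundus photographs as the core-phase safety results still to be reported. And repeating the analysis on Safety Sets 1 to 3 brings in the randomised DT-versus-granules period, where a comparison of new findings by arm would be most informative. Section 4 of the final SAP, which records departures from the protocol, gives no reason for treating this modality differently.

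**Working it through.** The plan states no figure to reproduce here. The check is a comparison of sections, followed by a short demonstration of what by-visit counts can and cannot show.

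**Baseline comparison by modality, final SAP Section 2.7.6**

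- Visual acuity (2.7.6.1): shift tables of increases and decreases from baseline at each visit.
- Slit lamp (2.7.6.2): shift to worst post-baseline, and by visit.
- Tonometry (2.7.6.3): changes from baseline, and a shift table at each time point.
- Lens photographs (2.7.6.4): shift of worst change in grade.
- Site fundus examination (2.7.6.5): shift to worst post-baseline.
- Colour fundus photographs (2.7.6.6): none.

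**What by-visit counts identify.** Take one eye side and one evaluation type. Let n0 eyes be imaged at baseline with a0 abnormal, and n1 of those eyes be imaged later with a1 abnormal. Among the n1 eyes, the number abnormal at baseline, b, lies between max(0, a0 − (n0 − n1)) and min(a0, n1). The number newly abnormal then lies between max(0, a1 − b_max) and min(a1, n1 − b_min).

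The documents give no abnormality rates and no numbers imaged. The figures below are therefore assumptions chosen to show the behaviour of the bounds, not estimates for this trial. The left case images the same 67 at both times. The right case images 210 at baseline and 67 later.

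| Assumed % abnormal, baseline then later | Same 67: a0, a1 → new | 210 then 67: a0, a1 → new |
|---|---|---|
| 10, 10 | 7, 7 → 0 to 7 | 21, 7 → 0 to 7 |
| 10, 20 | 7, 13 → 6 to 13 | 21, 13 → 0 to 13 |
| 5, 10 | 3, 7 → 4 to 7 | 10, 7 → 0 to 7 |
| 5, 20 | 3, 13 → 10 to 13 | 10, 13 → 3 to 13 |

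Worked case, second row, same 67: b = 7, so new lies between 13 − 7 = 6 and min(13, 67 − 7) = 13. With 210 at baseline, b_min = max(0, 21 − 143) = 0 and b_max = 21, so new lies between max(0, 13 − 21) = 0 and 13. In the last two rows 5% of 210 is 10.5, taken as 10; with 11 the final lower bound would be 2 instead of 3.

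Two things follow. The number newly abnormal is not fixed by the by-visit counts in any row, even when the same eyes are imaged at both times. Loss of eyes between visits can widen the range, but the problem does not depend on it: the first row is identical in both columns. A per-eye shift table gives the number exactly, for the eyes with both images.

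**The case against.** Other planned outputs carry much of the information. Section 2.7.6.6 itself plans findings listings, from which new findings can be picked out subject by subject. Protocol Section 10.6.1.3 lists the findings of patients with new or worsened clinically significant ocular abnormalities. Protocol Section 7.2.4.5 sends significant findings that qualify as adverse events to the adverse event page. The site examination has its own shift table. Detailed layouts sit in separate TFL shells that are not available here. All of this stands, and it limits the point to a missing summary. None of these outputs, as described, gives a count with a denominator of new centrally read abnormalities by arm: listings have no denominator, the site examination is a different reading (by default on Safety Set 4), and the adverse event route covers only findings that meet that definition.

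A reader might go further in three ways that the documents do not support.

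- That new findings cannot be told apart from old ones at all. The listings contradict this.
- That the imaged cohort falls to about a third. By 6 December 2017, 94 + 116 = 210 patients had been randomised, and on 24 June 2021 "67 patients are ongoing in the extension phase of the study", so 67/210 = 31.9% (67/216 = 31.0% against the planned maximum). But that date is about two and a half years after all patients had completed the core phase (18 December 2018). Photographs taken before Amendment 6 are read too, so patients who left before June 2021 can contribute at Week 25, end of core and Week 101. The number imaged at those visits is not given.
- That a shift table would show whether deferasirox causes retinal change. Both arms receive deferasirox, and the stated purpose is only to support the safety evaluation.

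It is also fair to say that the number of eyes with paired images is unknown. Central collection came in after the core phase had ended, and the plan for a listing of subjects with available images suggests that not everyone has them.

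**Conclusion.** The point holds as a reporting gap. The planned summary tables for centrally read fundus photographs give the prevalence of abnormality by timepoint and arm, not new abnormalities, which would have to be extracted from listings. This rests on the text of the final SAP alone; if the TFL shells already contain a shift table, the SAP text only needs to say so.

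No numerical size can be attached. The retention figure and the assumed rates are not measures of the gap. Its importance is modest: one secondary safety output, with no primary or key conclusion affected and no data lost. It is still worth correcting, because the output answers a regulatory request and the remedy is already used elsewhere in the same section.

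**What to change.** Add to Section 2.7.6.6 a shift table from baseline to worst post-baseline, by eye side, evaluation type and treatment arm, using the without/with abnormality categories already in that section. Restrict it to eyes with gradable images at both times. Report alongside it:

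- the number and percentage newly abnormal, with eyes without abnormality at baseline as the denominator;
- the number of eyes without a gradable baseline image.

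Produce it on the sets already named: Safety Set 4 and Safety Sets 1 to 3. State which baseline applies to patients who crossed over from DT. Section 2.1.5 uses the last value before granules for the entire granule period, while Section 2.7.7.1 uses the core-phase baseline for growth data. The choice decides whether a finding that arose on DT counts as new.

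The cost is a few extra tables once the four sets are counted, with no new data collection. The yield depends on how many eyes have paired images, which is why the count without a gradable baseline should be shown.
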